**Abbreviated Protocol: 20210065** 

Date: 22 March 2021 Page 3 of 37

#### 1. BACKGROUND AND RATIONALE

BLINCYTO® (blinatumomab) is a bispecific T-cell engager indicated for the treatment of relapsed or refractory (R/R) CD19-positive B-cell precursor acute lymphoblastic leukemia (ALL). A Risk Evaluation and Mitigation Strategy (REMS) with goals to mitigate the risks of cytokine release syndrome (CRS), neurologic toxicities, and preparation and administration errors, was identified at the time of approval of the biological license application (BLA). The REMS communication plan consists of REMS Letters for Healthcare Providers (HCPs, including physicians and nurses), REMS Letter for Hospital and Home Healthcare Pharmacists, and REMS Letter for Professional Societies; a REMS Fact Sheet for Healthcare Providers; dissemination of REMS information at scientific meetings; and a REMS program website. Previous REMS assessment surveys have studied three populations: prescribers such as medical doctors, physician assistants, and nurse practitioners; nurses; and pharmacists. Results from the 5-year REMS assessment (submitted December 2019) indicated that surveyed physicians, pharmacists and nurses demonstrated adequate knowledge of the risks of cytokine release syndrome and neurological toxicity associated with BLINCYTO. Surveyed pharmacists and nurses, however, had lower understanding of the risk of preparation and administration errors associated with the use of BLINCYTO. The present REMS assessment conducted 7 years after the launch of BLINCYTO in the US will assess awareness and knowledge of preparation and administration errors associated with BLINCYTO use among pharmacists and nurses.

#### 2. OBJECTIVES

The broad objective of this study is to determine the level of awareness of the risks and safety associated with BLINCYTO therapy and certain aspects of the BLINCYTO REMS Program among pharmacists and nurses who have used BLINCYTO for patients in the treatment of relapsed or refractory B-cell precursor acute lymphoblastic leukemia (ALL). The specific objective is to:

 Evaluate the awareness and understanding of the preparation and administration errors associated with BLINCYTO use among pharmacists who have prepared BLINCYTO, and nurses who have administered BLINCYTO.

## 3. STUDY POPULATION/SAMPLE SIZE/STATISTICAL ANALYSES PLANS

#### Study Design

An online cross-sectional survey will be conducted among pharmacists and nurses who have dispensed, prepared and/or administered BLINCYTO in the US in the past

Abbreviated Protocol: 20210065

Date: 22 March 2021 Page 4 of 37

12 months outside the clinical trial setting. Previous similar surveys were conducted at 18 months, 3 years and 5 years after the launch of BLINCYTO. This cross-sectional survey is being conducted 7-years after the launch of BLINCYTO in the US.

#### **Study Population**

Inclusion criteria include HCPs, defined as nurses (RNs, BSNs), and hospital and/or home healthcare pharmacists who have dispensed, prepared and/or administered BLINCYTO therapy to patients outside of the clinical trial setting in the past 12 months. HCPs or their immediate family members (eg, spouse, children, and/or parent) who are or were employed by Amgen, Naxion, or the FDA will be excluded from participation. HCPs who have been part of previous assessments (at 18 months, 3 years, and 5 years after the launch of BLINCYTO) will also be eligible to participate.

A list of HCPs targeted by the REMS Program will be matched to the survey vendor's Panels and/or other target sources to determine a list of respondents. All HCPs that are identified via these sources will be invited to participate in this survey.

#### Survey Pre-testing

The main data collection method for this assessment will be online surveys. Before actual data collection, Naxion will conduct telephone-assisted online pilot surveys with appropriate HCPs (eg, approximately 5 each of oncology nurses and hospital-based pharmacists) on the proposed survey questions. Pre--tests will be used to assess the survey research instrument for each of the following:

- Directionality: Confirm that all questions are clearly understood by pre-test respondents.
- Survey duration: An estimation of the average duration of the survey will assist in planning the duration of the actual study.
- Completeness: Confirm that the response options provided are exhaustive and that no reasonable response options are omitted from closed-ended list questions.
- Question order effects: Determine whether there are question order effects (influence of previous question text or response on a following question) that can be controlled for by re-ordering questions.

The findings from the pre-test will be used to improve the survey instrument and generate a final document for the survey.

Date: 22 March 2021 Page 5 of 37

## Survey Methodology

Healthcare providers will be initially invited to participate in the survey by email (recruitment material, Appendix B). Majority of the surveys will be administered online and supplemented with telephone surveys. For those HCPs that opt for responding by telephone, the survey will be administered using computer-assisted telephone interviewing (CATI). In addition, direct mail invitations to participate in the online survey and/or hard copy surveys will be used to reach our target of completed surveys.

Screening questions will be placed at the beginning of the survey in order to determine whether HCPs are eligible to take part in a study. HCPs deemed ineligible by these questions are then terminated from the survey.

All possible answers for each survey question (not including screening questions) will be randomized. Participants will not be allowed to return to questions or be allowed to skip ahead during the survey administration. The correct answer choices will be provided on a screen at the end of the online survey. If the survey is completed by telephone, the correct answer choices will be provided by mail.

## **Survey Questions**

The survey instrument includes questions about:

- screening and demographics
- the risk of preparation and administration errors associated with BLINCYTO use
- preparation instructions, access to checklists and Product Information/Package Insert (PI) in the workplace setting of pharmacists and nurses
- awareness and utilization of REMS materials.
- specific questions about preparation and administration errors including frequency of errors, medication errors (for example underdosing and overdosing), adherence to instructions and guidelines for change of infusion bags, and reconstitution of BLINCYTO.

The survey questions are included as Appendix A.

#### **Endpoints**

The main endpoint of interest in this assessment is the awareness of the risk of preparation and administration errors associated with use of BLINCYTO

#### Sample Size

The sample size for this assessment will be 200, including 100 pharmacists and 100 nurses. The precision for the estimates of the awareness of different endpoints specified above for samples sizes of 100 each for pharmacists and nurses, and a pooled

Abbreviated Protocol: 20210065

Date: 22 March 2021 Page 6 of 37

sample of 200 healthcare workers are shown in Table 1 below assuming 5% level of significance.

Table 1. Precisions for Sample Sizes of 100 and 200 at Varying Proportions With the Outcome and at 95% Confidence

Sample size	Proportion with outcome					
	10%	20%	30%	40%	50%	
100	0.059	0.078	0.090	0.096	0.098	
200	0.042	0.055	0.064	0.068	0.069	

#### **Descriptive Analyses**

Separate analyses will be performed for nurses and pharmacists, as well as a pooled analysis of the two groups to assess the participants' understanding of the preparation and administration errors associated with the use of BLINCYTO. Categorical variables will be summarized using frequencies and proportions while quantitative data will be summarized using means and standard deviation for normally distributed data and medians and interquartile range for skewed data. For each survey question, the proportion and 95% CI of each response option including the 'not sure' and 'I routinely look it up' response categories will be reported. For each knowledge question, the proportion of HCPs selecting the correct response and corresponding 95% CI will be calculated. Analyses for each of the objectives are described in detail below.

Results will be presented for each HCP type separately, as well as pooled. For the main endpoint of the study, the understanding of preparation and administration errors, an individual participant must correctly answer at least 75% of the items to be considered to have knowledge. Specifically, knowledge will be assessed as follows:

- Nurses: Must correctly identify at least 75% of Questions 7, 10, and 11 (ie, 6 out of 8 items) to be considered to have knowledge (see Appendix A)
- Pharmacists: Must correctly identify at least 75% of Questions 8, 10, and 11 (ie, 6 out of 8 items) to be considered to have knowledge (see Appendix A)

A threshold knowledge score and corresponding 95% CI will be estimated as the proportion of HCPs (by type and overall) having knowledge of preparation and administration errors. Furthermore, the proportion of respondents deemed to have knowledge (ie, the proportion of respondents who have correctly identified at least 75% of the items) will be evaluated against a pre-specified threshold of 80% of a given HCP type. The percentage of respondents above and below the threshold knowledge score

Abbreviated Protocol: 20210065

Date: 22 March 2021 Page 7 of 37

will also be calculated. Responses for questions related to preparation instructions and access to checklists and Product Information/Package Insert (PI) in the workplace setting and knowledge of indication for BLINCYTO will be described with proportions and 95% CIs for each response option. Similarly, proportions and 95% CIs will be reported for the awareness and use of the REMS materials (responses for Questions 15 to 32 in Appendix A).

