## Appendix A. Questionnaire

## Screening questions:

Have you personally prepared, dispensed, and/or administered BLINCYTO
therapy to patients outside of the clinical trial setting in the last 12 months?
(Select all that apply)

a. I have personally prepared BLINCYTO therapy outside the clinical trial setting	0	
b. I have personally dispensed BLINCYTO therapy outside the clinical trial setting	0	
c. I have personally administered BLINCYTO therapy outside the clinical trial setting	0	
d. None of the above	0	TERMINATE

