## **Survey questions:**

## **Key Risk Message Questions**

7. According to the BLINCYTO Prescribing Information/Package Insert, please answer if the following statements are true or false. If you are not sure, please select "not sure."

	BLINCYTO Preparation and Administration	True	False	Not sure
L1	Preparation and administration errors have occurred with BLINCYTO treatment.  NOTE: We are not asking whether you have personally seen these issues at your facility.	0	0	0
L2	The recommended dose for BLINCYTO is based on patient body surface area (BSA) for patients who weigh less than 45 kg and is fixed (ie, not based on BSA) for patients who weigh greater than or equal to 45 kg.	0	0	0
L3	Medication errors such as underdosing and overdosing can occur if BLINCYTO is prepared or administered incorrectly.  NOTE: We are not asking whether you have personally seen these issues at your facility.	0	0	0
L4	When preparing BLINCYTO, you should follow the preparation instructions provided in the Full Prescribing Information.	0	0	0
L5	The BLINCYTO infusion line or intravenous catheter should not be flushed when changing infusion bags because it can result in excess dosage.	0	0	0
L6	The use of BLINCYTO prepared with benzyl alcohol preservative is recommended for use in adult and pediatric patients across all weight ranges.	0	0	0

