## PROGRAMMING:

- 1) Ask NURSE respondents
- 2) Example Prescribing Information visual aid to be displayed on screen
- 3) Display rows L4 and L6 ONLY if Q1 answer includes "a"
- 4) Randomize order of rows

Abbreviated Protocol: 20210065

Date: 22 March 2021 Page 19 of 37

8. Based on the BLINCYTO Prescribing Information/Package Insert, please answer if the following statements are true or false. If you are not sure, please select "not sure."

	BLINCYTO Preparation and Administration	True	False	Not sure
L1	Preparation and administration errors have occurred with BLINCYTO treatment.	0	0	0
	NOTE: We are not asking whether you have personally seen these issues at your facility.			
L2	The recommended dose for BLINCYTO is based on patient body surface area (BSA) for patients who weigh less than 45 kg, and is fixed (ie, not based on BSA) for patients who weigh greater than or equal to 45 kg.	0	0	0
L3	Medication errors such as underdosing and overdosing can occur if BLINCYTO is prepared or administered incorrectly.  NOTE: We are not asking whether you have personally seen these issues at your facility.	0	0	0
L4	When preparing BLINCYTO, you should follow the preparation instructions provided in the Full Prescribing Information.	0	0	0
L5	Reconstitute BLINCYTO with IV Solution Stabilizer for Injection.	0	0	0

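### For nurses shown only six of the eight scored items, the 75% rule and the 6-out-of-8 count disagree on who has knowledge

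*Protocol*

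**What the plan says.** Section 3 (Descriptive Analyses) sets the general rule that "an individual participant must correctly answer at least 75% of the items to be considered to have knowledge". The nurse bullet makes it specific: "Nurses: Must correctly identify at least 75% of Questions 7, 10, and 11 (ie, 6 out of 8 items". The proportion of nurses who meet it is then compared with a pre-specified threshold of 80% for that type of provider.

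The programming notes under Question 7 in Appendix A say "Display rows L4 and L6 ONLY if Q1 answer includes" option a. In the screening question, option a is "I have personally prepared BLINCYTO therapy outside the clinical trial setting". Option c is "I have personally administered BLINCYTO therapy outside the clinical trial setting". Only the none-of-the-above option ends the survey, so a nurse who administered the drug but never prepared it is eligible.

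Section 2 states the target population as "among pharmacists who have prepared BLINCYTO, and nurses who have administered BLINCYTO". The protocol gives no separate denominator for nurses who see the shorter Question 7 and does not say how undisplayed rows are scored.

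**The concern.** The protocol offers the percentage and the count as the same pass mark. They are the same only for a respondent who sees all eight items. Nurses are targeted because they administer the drug, and the display condition exists because some of them will not have prepared it. Nurses who see the short version are therefore foreseeable.

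The rule defines the main endpoint. Under the printed count, a non-preparing nurse fails on a single error or a single not-sure answer, while a nurse who also prepares may miss two items. An analyst could follow either half of the bullet and cite the protocol for it. That choice could be made after the data are seen, and it could decide on which side of 80% the nurse result falls.

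**Working it through.** **Item count (Appendix A)**

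- Question 7 has six rows, L1 to L6.
- Question 10 is one item asked of everyone. Its number is not legible in the text I worked from; I identified it as the item directly before Question 11.
- Question 11 is one item asked of everyone.
- Full display: 6 + 1 + 1 = 8 items, and 0.75 × 8 = 6. The protocol's 6 of 8 is reproduced.
- Display without option a: L1, L2, L3, L5, Question 10 and Question 11, so 4 + 1 + 1 = 6 items.
- For this display, the count of six means 6/6 = 100%. The percentage gives 0.75 × 6 = 4.5, so at least 5 of 6, which is 83.3%.
- If the denominator is kept at eight and hidden rows are scored as not correct, the bar is again 6 of 6.

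The two versions differ for exactly one result: a non-preparing nurse with 5 of 6 correct.

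**Size**

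The protocol gives neither a per-item probability of a correct answer (p) nor the share of non-preparing nurses (f). Both are assumptions here. Items are taken as independent with equal p. Binomial pass probabilities:

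| p | at least 6 of 8 | 6 of 6 | at least 5 of 6 |
|---|---|---|---|
| 0.85 | 0.895 | 0.377 | 0.776 |
| 0.90 | 0.962 | 0.531 | 0.886 |
| 0.95 | 0.994 | 0.735 | 0.967 |

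Expected nurse proportion = (1 − f) × P(at least 6 of 8) + f × P(pass on six items). Each cell shows the printed count first, then 75% of the items shown:

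| p | f = 25% | f = 50% | f = 75% |
|---|---|---|---|
| 0.85 | 0.765 / 0.865 | 0.636 / 0.836 | 0.507 / 0.806 |
| 0.90 | 0.854 / 0.943 | 0.747 / 0.924 | 0.639 / 0.905 |
| 0.95 | 0.929 / 0.987 | 0.865 / 0.981 | 0.800 / 0.974 |

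The share at which the printed count brings the expected result to 80% solves (1 − f) × P(at least 6 of 8) + f × P(6 of 6) = 0.80:

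- p = 0.85: (0.895 − 0.80) / (0.895 − 0.377) = 0.095 / 0.518, about 18%.
- p = 0.90: (0.962 − 0.80) / (0.962 − 0.531) = 0.162 / 0.431, about 38%.
- p = 0.95: (0.994 − 0.80) / (0.994 − 0.735) = 0.194 / 0.259, about 75%.

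With 100 nurses and 100 pharmacists, the pooled proportion moves by half the nurse difference. At p = 0.90 and f = 50%, the nurse difference is 92.4 − 74.7 = 17.7 points, so the pooled difference is about 8.9 points.

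**The case against.** The item count is not in dispute. What can be contested is the consequence.

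- **The percentage is the dominant wording.** Section 3 states the rule as a percentage several times, and the count appears only as a parenthetical gloss that is exact for the full display. An analyst who applies 75% to the items shown asks for 5 of 6, and no nurse needs a perfect score. This stands. A reader might infer that the plan imposes a 100% bar on non-preparing nurses and biases the nurse result downward. The documents support that only if the printed count is applied, or if hidden rows are scored as not correct.
- **The effect size rests on assumptions.** This also stands. At p = 0.95 with half the nurses non-preparing, the printed count gives about 86%, still above 80%. Equal difficulty is doubtful too: L1, L3 and L4 are general statements, while L2, L5 and L6 test specific label content. One hidden row is of each kind, so the documents do not show which display is harder.
- **Scoring of skipped rows could be left to the SAP.** This holds only in part, because the protocol prints a count that conflicts with its own questionnaire.
- **The survey is descriptive.** It has a precision-based sample size, and item-level proportions are reported in any case. No data are lost under either reading. That limits the damage, but the comparison with 80% still uses the composite score.

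**Conclusion.** The point holds as an inconsistency in the scoring of the main endpoint. For nurses who did not report preparing the drug, the two halves of the nurse rule require 6 of 6 and 5 of 6, and the protocol does not say which governs. This follows from counting items and needs no assumption.

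The size is conditional. If the count is applied, the nurse and pooled proportions are pulled down by an amount set by the unknown share of non-preparing nurses. Under independent items of equal difficulty, the expected nurse proportion falls below 80% when that share exceeds about 18%, 38% or 75%, for p = 0.85, 0.90 and 0.95.

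A reader might also infer that applying the percentage makes the two displays comparable. It does not. With six items 75% cannot be met exactly, so the bar is 83.3%. At p = 0.90, equally knowledgeable nurses would still pass at 96.2% on the long display and 88.6% on the short one (89.5% and 77.6% at p = 0.85). The dependence on who prepares is reduced but not removed.

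**What to change.** In the nurse bullet of Section 3, replace the fixed count with: *at least 75% of the scored items displayed to that respondent (6 of 8 if option a of screening Question 1 was selected; 5 of 6 otherwise)*. Settle this before any responses are scored.

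Because pass rates still differ by display, report the nurse knowledge proportion separately for the two displays. Add a sensitivity analysis that scores every nurse on the six items all of them see (Question 7 rows L1, L2, L3 and L5, Question 10 and Question 11), with 5 of 6 as the pass mark.

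The cost is one sentence in the protocol, one line of scoring code and a small addition to the tables. The questionnaire and the sample size do not change. What is accepted in return is an 83% bar, in place of 75%, for nurses on the short display.

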#### PROGRAMMING:

- 1) Ask PHARMACIST respondents
- 2) Example Prescribing Information visual aid to be displayed on screen
- 3) Randomize order of rows
- The Full Prescribing Information/Package Insert contains the most complete instructions on BLINCYTO preparation (including admixing) and administration to minimize medication errors (including underdose and overdose).

(Select one answer)

a. True	
b. False	
c. I am not sure	

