#### PROGRAMMING:

1) Ask all respondents

Abbreviated Protocol: 20210065

Date: 22 March 2021 Page 20 of 37

11. Aseptic technique must be strictly observed when preparing or administering the BLINCYTO solution for infusion.

(Select one answer)

a. True
b. False
c. I am not sure

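### The pharmacist knowledge rule is stated as 6 of 8 items, but Questions 8, 10 and 11 hold only 7, so the effective pass mark is 86%, not 75%

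*Protocol*

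**What the plan says.** Section 3, Descriptive Analyses, gives a general rule for the main endpoint: "an individual participant must correctly answer at least 75% of the items to be considered to have knowledge". It then makes the rule specific to each type of respondent. For nurses: "Nurses: Must correctly identify at least 75% of Questions 7, 10, and 11 (ie, 6 out of 8 items". For pharmacists: "Pharmacists: Must correctly identify at least 75% of Questions 8, 10, and 11 (ie, 6 out of 8 items". Both bullets refer to Appendix A for the items. The proportion of respondents with knowledge is reported by type and pooled, and is compared with a pre-specified threshold of 80% of a given type.

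In Appendix A, Question 8 carries the instruction "Ask PHARMACIST respondents". Its rows run from L1 to L5, the last being "Reconstitute BLINCYTO with IV Solution Stabilizer for Injection". Its programming notes randomise the row order and make no row conditional. The next question, asked of all respondents, is one true/false/not sure statement that begins "The Full Prescribing Information/Package Insert contains the most complete instructions on BLINCYTO preparation". Question 11 is also one statement for all respondents: "Aseptic technique must be strictly observed when preparing or administering the BLINCYTO solution for infusion".

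**The concern.** The bullet in Section 3 is the operational definition of the main endpoint for half of the planned sample (100 pharmacists of 200). Its denominator does not match the questionnaire it cites. The nurse and pharmacist bullets give the same count, so a reader will take the two groups to be held to the same tolerance of two misses in eight. If the pharmacist scale is shorter, that equality does not exist, yet both groups are judged against one 80% threshold and combined in a pooled proportion.

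This matters for interpretation. Section 1 gives lower understanding of preparation and administration errors among pharmacists and nurses as the reason for this survey. A report that describes the pharmacist result as a 75% standard would understate how strict the test was.

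**Working it through.** **Inputs, from Appendix A**
- Question 8 (pharmacists): 5 rows, L1 to L5, all shown.
- Question 10 (all respondents): 1 item.
- Question 11 (all respondents): 1 item.
- Question 7 (nurses): 6 rows, L1 to L6. L4 and L6 are shown only to nurses who report having prepared the product.

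**Step 1: reproduce the stated count of 8.**
- Nurses shown every row: 6 + 1 + 1 = 8. This agrees with the nurse bullet.
- Pharmacists: 5 + 1 + 1 = 7. This does not agree with the pharmacist bullet.

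**Step 2: pass count**, the smallest whole number at or above 0.75 × items.

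| Group | Items | 0.75 × items | Pass count | Effective mark | Next score down | Misses allowed |
|---|---|---|---|---|---|---|
| Pharmacist, as stated | 8 | 6.00 | 6 | 6/8 = 75.0% | 5/8 = 62.5% | 2 |
| Pharmacist, as counted | 7 | 5.25 | 6 | 6/7 = 85.7% | 5/7 = 71.4% | 1 |
| Nurse, all rows shown | 8 | 6.00 | 6 | 6/8 = 75.0% | 5/8 = 62.5% | 2 |
| Nurse, L4 and L6 hidden | 6 | 4.50 | 5 | 5/6 = 83.3% | 4/6 = 66.7% | 1 |

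**Step 3: does the error change anyone's classification?** The 75% rule on 7 items requires 6. The literal count in the bullet requires 6. Counting the absent eighth item as wrong still requires 6 of the 7 real items. All three agree.

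**Step 4: illustration of what the shorter scale does.** The documents give no per-item accuracy, so a range is assumed, with independent and equally difficult items, each answered correctly with probability p.
- P(at least 6 of 7) = 7p⁶(1−p) + p⁷
- P(at least 6 of 8) = 28p⁶(1−p)² + 8p⁷(1−p) + p⁸

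At p = 0.85 the first is 0.396 + 0.321 = 0.717. The second is 0.238 + 0.385 + 0.272 = 0.895.

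| p | 6 of 7 | 6 of 8 |
|---|---|---|
| 0.80 | 57.7% | 79.7% |
| 0.85 | 71.7% | 89.5% |
| 0.90 | 85.0% | 96.2% |
| 0.95 | 95.6% | 99.4% |

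The two scales fall on opposite sides of 80% only for p between about 0.80 and 0.88.

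**The case against.** The strongest reply is that this is a clerical slip with no effect on the data. The governing rule is a minimum of 75%. On seven items the lowest score that meets it is 6, so 86% is simply the first attainable score above the minimum, and the endpoint is determinate. This stands as far as it goes: no pharmacist changes category. It does not answer the point that the protocol states a tolerance of two misses in eight, which this instrument cannot deliver.

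Second, a reader might infer from the illustration that the error would flip the pharmacist verdict against 80%. The documents do not support that. The comparison is with an eight-item pharmacist scale that Appendix A does not contain. The item probabilities are assumed, and the verdicts differ only in a limited range: at 0.80 both scales fall short, and at 0.90 both clear the threshold.

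Third, the unequal bars are not purely a pharmacist-versus-nurse matter. Nurses who have not prepared the product see six items and, under the 75% rule, may also miss only one. Section 3 plans no formal contrast between the groups, and the items differ by role by design. All of this stands. It means that correcting the pharmacist count will not by itself make the pooled standard uniform.

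Fourth, each knowledge question is also reported separately with a 95% CI, and the pre-test may still change the instrument. That limits the harm and makes correction easy, but the composite remains the main endpoint.

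Finally, in the text available to me the number of Question 10 is missing, so I identified it by its place between Questions 8 and 11. A lost row in Question 8 cannot be wholly excluded, but L1 to L5 run in unbroken sequence into the programming notes.

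**Conclusion.** The point holds. The pharmacist rule for the main endpoint gives 8 items where the questionnaire has 7, so the effective pass mark is 85.7% with one miss allowed, not 75% with two. The standard is misstated for one of the two respondent types, and the result is pooled and compared with 80% as if the rule matched the nurse rule. The size is certain for the count and the pass mark, and nil for the classification of individuals. Any effect on the 80% verdict relative to an eight-item scale is illustrative and rests on independence and equal difficulty.

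A reader might also infer that an eighth pharmacist item was dropped from Question 8. Nothing in the protocol shows this. The nurse count carried over into the pharmacist bullet would explain the figure at least as well. The sponsor has to say whether the count or the questionnaire is right.

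**What to change.** Reconcile the pharmacist bullet in Section 3 with Appendix A before fielding, in one of two ways:

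1. If seven items are intended, restate the rule as 6 of 7 items (86%) and print each group's effective pass mark beside its comparison with 80%.
2. If eight were intended, add one pharmacist row to Question 8 so that 6 of 8 holds.

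In either case, supplement the pooled result with a score on the five items that every respondent sees: rows L1 to L3 of Question 7 or 8, and Questions 10 and 11. Row L4 should stay out of that score, because some nurses do not see it and the denominator would vary again. On five items the 75% rule means 4 of 5 (0.75 × 5 = 3.75), or 80%. The score should be a supplement and not a replacement, because it omits the role-specific items on line flushing and reconstitution.

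The cost is a wording correction or one added survey row, plus one small extra analysis. With the first option, the stated standard becomes visibly less uniform across groups. An item that was never asked cannot be recovered after fielding, so the choice has to be made beforehand.
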